6.2 Secondary analyses

Secondary feasibility outcome, as measured by questionnaire (percentage of participants with high satisfaction tDCS and training equipment), will be analyzed similarly to the primary outcome. The point estimate and the 95%CI of the feasibility criterion (according to the Agresti & Coull formula) will be presented.

Data distributions of the questionnaire items will be visually assessed for normality using q-q plots.

Data on behavioral tasks from all participants (included at randomization and completed post-assessment) will be analyzed using linear mixed models. (See details below)

Additionally, a subgroup analysis will include only those participants who successfully completed two-thirds of the home-based sessions (thus fulfilling the criterion for feasibility; per protocol analyses).

Training task effects

Using linear mixed models (random intercept models accounting for clustering of measures within individuals), the performance of the letter updating task over the study period including all measures after start of intervention V2-V9 will be used as dependent variable, stimulation group (tDCS, sham) as factor, and letter updating performance at pre-assessment as well as age and sex as covariates. The time point of measure will also be included as variable and will be modelled as categorical variable or as continuous variable that reflects the changes over time. Additionally, an interaction term for group X time point will be included to model differential changes over time in both groups. The letter updating task score at post assessment will be evaluated between treatment groups based on this regression model via marginal means to examine immediate training effects. The letter updating task

score at fu assessment will be evaluated between treatment groups based on this regression model via marginal means to examine sustained training effects.

Transfer task effects

Effects on the n-back task will be evaluated using similar linear mixed models (random intercept models accounting for clustering of measures within individuals). The performance of the n-back task will include measures after start of intervention V8, V9 (post and fu assessment), will be used as dependent variable, stimulation group (tDCS, sham) as factor, and letter updating performance and n-back-performance at pre-assessment as well as age and sex as covariates. Additionally, the time point of the measure and the interaction between group and time point will be included as fixed effects. The n-back score at post assessment will be evaluated between treatment groups based on this regression model via marginal means to examine immediate transfer effects. The n-back score at fu assessment will be evaluated between treatment groups based on this regression model via marginal means to examine sustained transfer effects. We will assess percent correct and d-prime in two different linear mixed models.

Type of link function (logistic, linear, ordinal) will depend on the scaling of the dependent variable. In case of skewed continuous data, variables will be transformed before analysis.

All secondary analyses will be done using the full analysis. All secondary analyses will be done in an exploratory framework.

Effect estimates and corresponding 95%CI will be reported for each outcome for time points post and follow-up (V8, V9).

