1.5 Sample Size Calculation

As the primary goal of this study will be to assess feasibility, and as it is recommended to employ results of feasibility trials for sample size calculation of a planned subsequent trial (Hagen et al., 2011), we chose a sample size of N = 30 (Rahbek et al., 2017). To infer feasibility, the lower bound of the 95 % confidence interval of the proportion of participants who fulfilled the feasibility criterion needs to be at 60 %. Thus, 76 %, i.e., n = 23 participants will have to meet the feasibility criterion.

With 15 participants per stimulation group (anodal vs. sham stimulation), we will be able to scope the general feasibility of this home-based intervention and explore descriptively the benefit of anodal tDCS over sham with regard to performance after the training on the trained and untrained working memory tasks to obtain estimates of effect sizes for power calculations of future randomized controlled trials (Elmasry et al., 2015; Antonenko et al., 2018). Using an independent t-test with a two-sided significance level of 0.05 and a power of 80 % we will be able to demonstrate an effect of Cohen's d = 1.06 or higher on behavioral performance. Since this effect size is high and might be unrealistic, we use the secondary analyses on efficacy measures solely exploratory to inform future trials.

2 Analysis sets

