2.1 Definitions

The **full analysis set** will consist of all participants who received at least one day of intervention. In case participants withdraw informed consent after baseline assessment, they will be considered as screening failures and therefore will not be included in the full analysis set. The **per protocol analysis set** comprises all subjects who successfully completed two-thirds of the home-based sessions (thus fulfilling the criterion for feasibility). Safety measures will be assessed during tDCS intervention and all participants who received at least one day of intervention will be included according to their actual treatment in **the safety analysis set**.

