2.2 Application

The efficacy analysis regarding the effect of tDCS-accompanied training on working memory performance will be done using the full analysis set. For the safety analysis, analysis will be done in the safety analysis set, which is the same as the full analysis set.

3 Trial centres

Participants will be recruited in one centre: Greifswald.

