4.4 Safety Outcomes

Safety parameters are assessed via self-report questionnaire every third day of training (V4, V7). The questionnaire was adapted from Antal et al. (2017) and includes intensity ratings with regard to itching, pain, burning, warmth/heat, metallic/iron taste, fatigue/decreased alertness and other sensations.

5 Handling of missing values

Primary outcome of this trial is the feasibility of the intervention. For the primary outcome no missing value imputation will be done, since missing information is related to non-adherence of the participants. Secondary efficacy outcome analyses will be done using complete data without any imputation, due to the small sample size and the exploratory framework of the study.

6 Statistical analyses

For all analyses (including the analysis of the primary outcome) appropriate descriptive statistics (absolute score, mean, standard deviation, median, interquartile range, absolute and relative frequencies) depending on the scale and distribution of the outcome variable will be presented.

Statistical analyses will be divided to analyze

- 1. feasibility
- 2. training effects on letter updating task (at post and 1 month follow-up)
- 3. transfer effects on n-back task (at post and 1 month follow-up)

Training and transfer measures will be corrected for performance at pre-assessment.

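### Section 6.2 limits the behavioural mixed models to post-assessment completers, although the SAP assigns the same models to the full analysis set

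*SAP*

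**What the plan says.** Four statements in the SAP set the population for the behavioural models.

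- Section 2.1: the full analysis set "will consist of all participants who received at least one day of intervention".
- Section 2.2: the efficacy analysis of working memory "will be done using the full analysis set".
- Section 6.2, opening part: "Data on behavioral tasks from all participants (included at randomization and completed post-assessment) will be analyzed using linear mixed models".
- Section 6.2, closing part: "All secondary analyses will be done using the full analysis".

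The outcomes differ between the two tasks. For letter updating, performance "including all measures after start of intervention V2-V9 will be used as dependent variable". For the transfer task, "The performance of the n-back task will include measures after start of intervention V8, V9 (post and fu assessment").

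Section 5 adds: "Secondary efficacy outcome analyses will be done using complete data without any imputation". Section 1.5 gives the purpose of the behavioural comparison, which is "to obtain estimates of effect sizes for power calculations of future randomized controlled trials".

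**The concern.** The same models are given two populations. Someone who received at least one session but did not attend V8 belongs to the analysis under 2.1, 2.2 and the end of 6.2, and is removed by the opening part of 6.2. Two analysts could each follow the SAP and analyse different people, and the choice could be made after the data are seen.

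The completer rule also conditions on something that happens after randomisation. If missing V8 is related to performance and the losses differ between arms, the group contrast among completers can be biased. In the letter-updating model the rule discards outcome data that were actually collected. What is at stake is possible bias in the effect sizes passed on to future trials. Precision, the primary feasibility outcome and confirmatory claims are not at issue.

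**Working it through.** **The plan's own figure.** The only design figure for these analyses is the detectable effect in section 1.5 (15 per group, two-sided 0.05, 80% power, d = 1.06). With a noncentral t on 28 degrees of freedom and noncentrality d × √(15/2) = 1.06 × 2.739 = 2.90, power is 80.0%, and exactly 80% is reached at d = 1.0598. The figure reproduces. The point made here does not depend on it.

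**Can the texts be reconciled?**

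- The V8 condition cannot describe the per-protocol analysis. Section 6.2 introduces that afterwards as an additional analysis and defines it by two-thirds of sessions, not by V8 attendance.
- The closing sentence of 6.2 omits the word set, but 2.2 is explicit.
- Complete data in section 5 can mean completers, which contradicts 2.2, or observed data without imputation, which contradicts the opening of 6.2. It settles nothing. A likelihood-based mixed model uses partial series without imputing.

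**What is lost.** Letter updating has 8 outcome scores per person (V2-V9), at most 30 × 8 = 240. A participant who leaves before V8 has 1 to 6 observed scores. With an assumed 1 to 6 such participants, the rule discards from 1 × 1 = 1 to 6 × 6 = 36 observed scores. Someone who missed V8 but came to V9 loses the V9 score as well. In the n-back models, with outcomes at V8 and V9 only, the rule matters only for that last kind of participant.

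**Effect on the letter-updating V8 contrast.** Simulation, 2000 trials per scenario.

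- From the SAP: 15 per arm; random-intercept model; group × time; pre-assessment score, age and sex as covariates. Time was taken as categorical, one of the SAP's two options.
- Assumed: REML fit; between-person SD 3 lists; residual SD 2, also for the pre-assessment score; no true effect; the lowest V2-V7 performers miss V8 and V9.

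| Lost before V8 | Completers | All observed | Difference (MC SE) |
|---|---|---|---|
| 1 in one arm only | 0.103 | -0.015 | 0.118 (0.003) |
| 2 in one arm only | 0.216 | -0.015 | 0.231 (0.004) |
| 3 in one arm only | 0.322 | -0.014 | 0.336 (0.005) |
| 1 per arm | -0.019 | -0.016 | -0.003 (0.004) |
| 2 per arm | -0.009 | -0.010 | 0.001 (0.006) |
| 1 versus 2 | 0.099 | -0.016 | 0.115 (0.005) |
| 1 versus 3 | 0.213 | -0.015 | 0.228 (0.006) |

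The all-observed estimates lie within Monte Carlo error of 0 (MC SE 1.0/√2000 ≈ 0.02). The model standard error is 0.99 to 1.03 under both rules. Total SD is √(3² + 2²) = 3.6 lists, so 0.336 lists is 0.336/3.6 ≈ 0.09 SD.

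**Sensitivity.**

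- Pre-assessment noise: with three lost in one arm, the shift runs from 0.11 lists (noise SD 1) to 0.53 lists (noise SD 3), the latter 0.53/3.6 ≈ 0.15 SD. With one lost in one arm and noise SD 1 it is 0.045.
- V8 missed but V9 attended: the V9 contrast shifts by 0.114 (one lost in one arm) or 0.333 (three lost in one arm).
- Drop-out driven by the unseen V8 score: both rules are biased. Completers versus all observed give 0.221 versus 0.139 (one lost in one arm), 0.615 versus 0.390 (three lost in one arm), and -0.015 versus -0.012 (one lost per arm).

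**The case against.** The case for treating this as minor is reasonable. The analyses are declared exploratory, and nothing changes unless someone misses V8. Balanced losses do no harm, and the largest main-scenario shift is a third of a standard error, reached only if three of the weakest performers leave one arm and none leave the other. The size also depends on how well the pre-assessment score predicts later performance, which the SAP does not state. All of this stands, and it limits the weight of the point.

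A second argument is that section 5 and the opening of 6.2 together show a deliberate completer analysis, so that the label in 2.2 is the slip. That reading is possible, but it confirms that the SAP contradicts itself. It also leaves the less defensible rule in force, because observed scores are dropped on a post-randomisation criterion. The all-observed rule is not free of bias when drop-out depends on unseen scores, though in the scenarios with unequal losses it is less biased than the completer rule.

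Two drafting objections are fair. Removing only the V8 condition would leave a reference to randomisation that still differs from the full analysis set. REML fits the linear models but not the logistic or ordinal versions that 6.2 permits. The fix allows for both.

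**Conclusion.** The contradiction is in the text, and no other passage of the SAP resolves it. Its numerical effect is uncertain and probably small. Under the assumptions above, the V8 letter-updating contrast moves by 0 to 0.34 lists (0 to about 0.09 SD), and by up to about 0.15 SD with a noisier pre-assessment score. These figures rest on assumed variances, an assumed drop-out count and low performers leaving; the SAP supplies none of these. The n-back models are affected only by participants who miss V8 and attend V9. The SAP should be corrected because the effect estimates are what these analyses are meant to deliver, and the people behind them should be fixed in advance.

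**What to change.** In section 6.2, replace the parenthesis that defines the population with a reference to the full analysis set, removing the post-assessment condition. Then specify:

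- Letter updating: all full-analysis-set participants with a pre-assessment score and at least one score from V2 to V9.
- N-back: those with the required pre-assessment scores and at least one of V8 and V9.
- Estimation: REML for the linear models, no imputation, with the missing-at-random assumption stated. If another link is used, name the corresponding likelihood method.
- Section 5: say that complete data means all observed data without imputation.
- The completers-only analysis as a named sensitivity analysis, with the numbers missing V8 and V9 reported by arm.

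The cost is SAP wording and negligible analysis work; no new data are needed. The downside is that the V8 and V9 contrasts will then rely on missing at random and on the random-intercept covariance, neither of which 30 participants can verify.

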1.4 Study Design

The TrainStim-Home trial is a randomized, double-blind, placebo-controlled monocenter study. The experimental group receives a six-session cognitive training intervention over two weeks, accompanied by tDCS over the left dorsolateral prefrontal cortex (DLPFC). The intervention of the control group consists of the same six-session cognitive training combined with sham stimulation.

Random allocation to experimental and control groups, respectively, will be performed with a 1:1 ratio. Stratified block randomization will be used. Strata will be chosen according to age (60-70 and 71-80 years) and initial performance in the letter updating task (≤ 5 , $\geq 5/25$ correctly recalled lists). After successful completion of telephone screening and baseline assessment (defined as meeting all eligibility criteria) and giving written informed consent, participants will be divided into four groups according to the age and performance strata. For the randomization we will use the blockrand package

in R¹.

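### The performance stratifier, the V0 letter updating score, is in no efficacy model; adding it beside the V1 score would probably tighten the exploratory training estimates a little

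*SAP*

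**What the plan says.** Section 1.4 of the SAP sets out stratified block randomisation: "Strata will be chosen according to age (60-70 and 71-80 years) and initial performance in the letter updating task", the latter cut at about 5 of 25 lists. Participants are sorted into the four strata once telephone screening and the baseline assessment are complete. Table 1 labels V0 as baseline and V1 as pre, and marks the letter updating task at both, as well as at V2 to V7, V8 and V9.

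Section 6 states the general rule: "Training and transfer measures will be corrected for performance at pre-assessment". Section 6.2 applies it. The training model takes letter updating at V2 to V9 as the outcome, with group, time point, their interaction, and "letter updating performance at pre-assessment as well as age and sex as covariates". The transfer model uses "letter updating performance and n-back-performance at pre-assessment as well as age and sex as covariates". The V0 letter updating score is neither an outcome nor a covariate in either model, and no reason is given for leaving it out.

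Section 1.5 gives the efficacy part the purpose of supplying effect-size estimates for planning later trials. Section 6.2 declares these analyses exploratory and promises estimates with 95% confidence intervals at V8 and V9.

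**The concern.** A factor that steered the allocation is normally carried into the analysis. Here one of the two stratifiers, age, is in the models. The other, initial letter updating performance, appears only through a later score on the same task. Sex, which is not a stratifier, is included.

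The V0 score is also a second pre-treatment reading of the training outcome, already scheduled for both arms. With 15 participants per arm, the precision of the group contrast is the main thing the efficacy part can deliver. An unused pre-treatment measure of the outcome may therefore cost some of it. The choice should be fixed in advance, because picking the baseline score after the data have been seen invites selection.

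**Working it through.** **Inputs from the SAP.** The size is "With 15 participants per stimulation group (anodal vs. sham stimulation", so N = 30, and allocation "will be performed with a 1:1 ratio". The strata are age band and initial letter updating performance (section 1.4). The model covariates are those in section 6.2. The SAP gives no correlation between V0, V1 and later scores, so every correlation below is an assumption.

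**The plan's own figure.** Section 1.5 works as follows: "Using an independent t-test with a two-sided significance level of 0.05 and a power of 80"%, giving "d = 1.06 or higher on behavioral performance". A noncentral-t calculation with 15 per arm returns d = 1.0598, with power 80.0% at d = 1.06, so the figure reproduces. It uses no covariates and is not touched by this point.

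**Large-sample formula.** Write r01 for the V0–V1 correlation, and r0y and r1y for the correlations of V0 and V1 with the post score.

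- Residual variance with V1 only: 1 − r1y².
- With V0 and V1: 1 − R², where R² = (r0y² + r1y² − 2·r0y·r1y·r01) / (1 − r01²).
- CI width ratio: √[(1 − R²) / (1 − r1y²)].
- With the V0/V1 mean as the single baseline: residual variance 1 − [(r0y + r1y)/2]² / [(1 + r01)/2].

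*Equal correlations of 0.7.* V1 only: 1 − 0.49 = 0.51. Both: 1 − 2(0.49)/1.7 = 0.424. Ratio √(0.424/0.51) = 0.911.

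*V0 redundant given V1 (r01 = 0.7, r0y = 0.49, r1y = 0.7).* R² = (0.2401 + 0.49 − 0.4802)/0.51 = 0.49, so the residual variance stays at 0.51 and the ratio is 1.00. With the mean: 1 − 0.595²/0.85 = 0.583, ratio √(0.583/0.51) = 1.07, so the interval is about 7% wider.

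**Small-sample check.** There were 5,000 simulated trials per scenario, each with N = 30, stratified blocks of 4 on dichotomised V0 and age, and a single-time-point ANCOVA with group, age, sex and the baseline term shown. CI widths are relative to the V1-only model. The last column is the coverage of the V1-only model.

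| r01, r0y, r1y | Add V0, large sample | Add V0, N = 30 | Add stratum only, N = 30 | Mean replaces V1, N = 30 | Coverage, V1 only |
|---|---|---|---|---|---|
| 0.5, 0.5, 0.5 | 0.943 | 0.956 | 0.976 | 0.938 | 95.1% |
| 0.7, 0.7, 0.7 | 0.911 | 0.925 | 0.967 | 0.905 | 95.7% |
| 0.8, 0.8, 0.8 | 0.896 | 0.911 | 0.972 | 0.892 | 95.4% |
| 0.9, 0.9, 0.9 | 0.881 | 0.898 | 0.985 | 0.879 | 96.1% |
| 0.7, 0.49, 0.7 | 1.000 | 1.018 | 1.012 | 1.065 | 94.9% |
| 0.8, 0.64, 0.8 | 1.000 | 1.019 | 1.013 | 1.082 | 95.0% |
| 0.8, 0.6, 0.7 | 0.996 | 1.014 | 1.010 | 1.016 | 95.4% |

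Adding continuous V0 narrows the interval by 4% to 10% in the first four rows and widens it by 1.4% to 1.9% in the last three. The mean does slightly better than adding V0 when the two scores are equally informative, but loses 2% to 8% when V0 is the weaker predictor. Adding only the binary stratum moves the width by about −3% to +1%.

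**The case against.** The strongest reply is that nothing in the SAP is contradictory. Adjusting for the last pre-treatment value of the outcome as a continuous covariate is conventional ANCOVA, and sections 6 and 6.2 prescribe it consistently. This stands: the omission is a missed refinement, not a mistake of method.

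Four stronger readings are tempting, and the documents do not support them.

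- *That the stratification is ignored, so the intervals are invalid.* Age is in both models, and V1 is the same task as the performance stratifier. Simulated coverage with V1, age and sex was 94.9% to 96.1%. V1 also does most of the work: dropping it as well made the interval 1.14 to 2.28 times as wide, with coverage of 96% to 99%.
- *That the intervals are certainly too wide.* This depends on correlations the SAP does not report. If V0 mainly reflects first exposure to the task, it may add nothing once V1 is known.
- *That averaging V0 and V1 is the natural remedy because it saves a degree of freedom.* The mean forces equal weights and loses precision when V1 is the better predictor. A practice gain from V0 to V1 does not bias the group contrast, but people may differ in that gain, which can make V0 less informative.
- *That the n-back estimates would gain too.* That model already holds the n-back pre-score and V1 letter updating, and no gain from V0 has been shown.

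The exploratory label lowers the weight of the point but does not remove it, since estimation is the stated purpose of this part.

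**Conclusion.** The point holds as a low-severity matter of precision. The V0 letter updating score, which by the timing in section 1.4 is the performance stratifier, enters no model. There is no bias, and coverage stays near nominal. The intervals for the training effects are probably somewhat wider than they could be: adding V0 would change their width by between about 10% narrower and 2% wider.

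The word probably rests on the score being short. If lists are treated as independent, a participant whose true rate sits at the 5/25 cut has a sampling SD of √(25 × 0.2 × 0.8) = 2 lists in one session, so a second reading would usually add information. The SAP gives no reliability figure to confirm this.

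Three further assumptions apply. Initial performance is read as V0 from the timing, since the visit is not named. The correlations are assumed. The simulations use a single-time-point ANCOVA, not the planned mixed model over V2 to V9. The primary feasibility analysis and the stated d = 1.06 are unaffected.

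**What to change.** - **Section 6.2, training model:** add the continuous V0 letter updating score as a further covariate, beside the V1 score, age and sex. Keep V1 as a separate term and do not substitute the V0/V1 mean.
- **Section 6:** align the general sentence on correction for pre-assessment performance, so that it covers the V0 letter updating score as well.
- **Section 1.4:** name V0 as the visit that supplies initial performance.
- **Section 6.2, transfer model:** adding V0 letter updating would serve only consistency with the stratification. If it is added, say so and claim no precision gain.

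The cost is a few words of SAP text, no new data and one degree of freedom: in the single-time-point ANCOVA, 30 − 5 = 25 residual degrees of freedom become 30 − 6 = 24. The worst simulated loss from adding V0 was about 2% in interval width.
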